**Consent, Screening, and Baseline Assessments.** Students who are interested in participating in the study will be contacted via study personnel. Participants will be given a brief overview of the study and its purpose and will be initially screened for eligibility using a standardized screening checklist. If the individual meets the inclusion and exclusion criteria, they will be invited to participate in the study. Participants will be given a list of instructions prior to their assessment. While participants should not be taking any routine prescription medications as part of the inclusion criteria, they will be told to abstain from taking any other types of medications including nutraceuticals, over-the-counter medications, vitamins, supplements 24 hours prior to coming to their appointment. Caffeine and alcohol should also not be consumed within 10 hours of their appointment. They will be instructed to get at least 6 hours of sleep the night prior and to only consume water prior to their scheduled visit.

At the research office, study personnel will explain the requirements, re-screen the participant, and review the consent form with each individual in a private room and obtain signed consent. After consenting, the participant will be asked to provide a urine sample which will be analyzed immediately onsite for potentially impairing or illicit drugs via a rapid urine test. If the individual tests positive for any potentially impairing substance, they will not be able to participate in the study. Anyone who tests positive for a drug will be referred to the Carruth Center on campus. If a participant's sample tests negative, they will then be allowed to practice on the driving simulator for approximately 10 minutes prior to engaging in any other study activities. This is necessary as some individuals who are prone to motion sickness may experience brief, mild nausea (e.g., simulator sickness). If there is evidence of simulator sickness, the individual will not be able to participate in the study, as they will likely not be able to complete the

protocol. Any reasons as to why an individual is not eligible to participate will be documented in a screening log. If no simulation sickness is observed, the student will then take the standardized and pilot-tested baseline survey regarding their demographics, health (including body mass index), and driving history along with the VAMS, SSS, TMT, DSST, PVT, and SRT tests.

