individuals will undergo a driving simulation and all participants will drive the same course. The simulator presents the individual with real life driving scenarios and is equipped with screens, a steering wheel, signals, and pedals (Figure 2). The participant will be instructed to drive the course for 25-35 minutes (this includes a practice drive and brake reaction time (BRT)). They will be instructed to follow normal driving rules, follow speed limits, and maintain constant speed and position within the lane, and brake when necessary. The simulation will include highway, suburban, rural, and urban driving scenarios which will incorporate turns, changes in speed, and avoidance of cars/pedestrians;

this course sequence and times were chosen to minimize simulator sickness. The simulator can monitor numerous aspects of drivers' performance and collect the data which is then downloaded and analyzed. Since we are investigating sedation and potential impairment, BRT, lateral position in the lane, lane departures, and collisions are the most telling performance measures. After the simulation, participants will retake the VAMS, SSS, TMT, DSST,

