**Table 2. Overview of proposed variables to be collected and for CBD studya**

Aim	Variables	Source
	Socio-demographics, driving history, health	Baseline questionnaire
Aim 1. Determine the effects of CBD on the driving performance of healthy adults aged 18-30 years.	
Driving performance
 
 
Number of lane departures
 
Number of collisions
 
Mean brake reaction time to stimuli
 
Mean standard deviation of lateral position in lane under consistent speed
 
	Driving simulation
Aim 2. Determine the effects of CBD on participants psychological status and cognitive function.	
Sedation
 
 
Self-reported sleepiness
 
Mental sedation: Sum of scores from questions 1,4,11,13 on VAMS—higher scores indicate more mental sedation
 
Physical sedation: Sum of scores from questions 3,5,6,16 on VAMS—higher scores indicate more physical sedation
 
 
Cognitive function
 
 
Number of symbols completed within 60 seconds
 
Number of correct symbols completed within 60 seconds
 
Time to accurately complete Part A and Part B
 
Mean reaction time to stimuli
 
Mean reaction time to stimuli
 
	
SSS VAMS
 
VAMS
 
DSST
 
TMT
 
PVT SRT

Aim 3. Determine the relation of driving performance to changes in psychological and cognitive status.	Correlation between variables in Aims 1 and 2	Driving simulation outcomes, SSS, VAMS, DSST, TMT, PVT, SRT

a: All measures will be assessed between treatment and placebo groups. DSST, SSS, TMT, PVT, SRT and VAMS scores will also be compared within subjects to gauge changes overtime.

correlated with psychological or cognitive testing measures. Data will also be analyzed via sex as well.

As one can see, there is minimal risk to participants. There is no direct benefit to participants. However, there are potential benefits to society that offset the potential risks of this study, which are minimal. The findings of this study will be extremely informative to the public, medical providers, policy makers, and public health practitioners.

Cannabidiol is commonly used drug, yet its effects in healthy populations are virtually unknown. Thus, the risk vs. benefit is reasonable.

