**Sample Size** – We conducted an analysis to ensure adequate sample size and power. The analysis was based on mean reaction time, which is one of the primary outcomes between groups. A total sample size of 26 students with a large effect size of 0.7 and  $\alpha=0.05$  using a two-sided, two-sample equal variance t-test achieves 80% power to reject the null hypothesis of equal means. Thus, our total sample size (N=40) should be more than adequate for this study.

**Data Safety Monitoring** – A Data Safety Monitoring Board will not be appointed for this study unless required.

 Table 2. Overview of proposed variables to be collected and for CBD studya

Aim	Variables	Source
	Socio-demographics, driving history, health	Baseline questionnaire
Aim 1. Determine the effects of CBD on the driving performance of healthy adults aged 18-30 years.	Driving performance 
 
Number of lane departures
 
Number of collisions
 
Mean brake reaction time to stimuli
 
Mean standard deviation of lateral position in lane under consistent speed
 
	Driving simulation
Aim 2. Determine the effects of CBD on participants psychological status and cognitive function.	Sedation 
 
Self-reported sleepiness
 
Mental sedation: Sum of scores from questions 1,4,11,13 on VAMS—higher scores indicate more mental sedation
 
Physical sedation: Sum of scores from questions 3,5,6,16 on VAMS—higher scores indicate more physical sedation
 
 Cognitive function 
 
Number of symbols completed within 60 seconds
 
Number of correct symbols completed within 60 seconds
 
Time to accurately complete Part A and Part B
 
Mean reaction time to stimuli
 
Mean reaction time to stimuli
 
	SSS VAMS VAMS DSST TMT PVT SRT
Aim 3. Determine the relation of driving performance to changes in psychological and cognitive status.	Correlation between variables in Aims 1 and 2	Driving simulation outcomes, SSS, VAMS, DSST, TMT, PVT, SRT

a: All measures will be assessed between treatment and placebo groups. DSST, SSS, TMT, PVT, SRT and VAMS scores will also be compared within subjects to gauge changes overtime.

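### Every participant drives the simulator before dosing, but the plan records no driving measure from that drive, so the primary comparison forgoes a baseline covariate and some precision

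*Combined protocol and SAP*

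**What the plan says.** Under Study Design & Methodology, the consent, screening and baseline paragraph says of participants with a negative urine test that "they will then be allowed to practice on the driving simulator for approximately 10 minutes prior to engaging in any other study activities". The reason given is to find people prone to simulator sickness. The baseline assessments that follow are a survey (demographics, health, driving history) and the six tests: VAMS, SSS, TMT, DSST, PVT and SRT. No driving measure is listed. Randomization and dosing come afterwards.

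The driving outcomes come from the 25–35-minute simulation held 120 minutes after dosing. That session has its own practice drive and brake reaction test. The design overview assigns the simulator to between-group effects and the test battery to both within-person and between-group effects. The footnote to Table 2 agrees: "DSST, SSS, TMT, PVT, SRT and VAMS scores will also be compared within subjects to gauge changes overtime". Driving is not among the measures it names.

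The between-group analysis is a t-test and/or ANOVA, or a Mann-Whitney test. No covariate is prespecified. The methodology section allows models to be adjusted if differences between the arms are seen.

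On what the simulator can do, the Intervention paragraph says it can monitor driving performance and "collect the data which is then downloaded and analyzed". On sample size, the SAP says "The analysis was based on mean reaction time, which is one of the primary outcomes between groups" and concludes that "our total sample size (N=40) should be more than adequate for this study".

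**The concern.** Each secondary test has a pre-dose and a post-dose value; the primary driving outcomes have only a post-dose value. Drivers can be expected to differ in habitual weaving and braking speed. With one post-dose value per person, all of that spread stays in the error term of the arm comparison. A pre-dose value from the same simulator could remove part of it, and each participant is already in the simulator before dosing.

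The provision for adjustment does not fill the gap. It is triggered by observed differences, and pre-dose simulator performance cannot be one of them because no measurement of it is planned.

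What is at stake is the width of the confidence interval for the driving effect. The trial looks for possible harm, so a null result with a wide interval would say little about whether driving is affected.

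**Working it through.** **Inputs from the documents.** Standardized effect 0.7; two-sided alpha 0.05; two-sample equal-variance t-test; 40 participants, 20 per arm (SAP, Sample Size; Allocation, Randomization and Blinding).

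**Input not in the documents.** The correlation r between a pre-dose driving measure and its post-dose counterpart. It is assumed, and varied from 0.1 to 0.7. No dropout is assumed.

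**Step 1: the plan's own figure.** The SAP states: "A total sample size of 26 students with a large effect size of 0.7 and" a two-sided alpha of 0.05 "achieves 80% power to reject the null hypothesis of equal means". With n per arm, the noncentrality is 0.7 × √(n/2) on 2n − 2 degrees of freedom.

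- n = 13 (26 in total): noncentrality 0.7 × √6.5 = 1.785, df 24, critical t 2.064, power 40.3%. The stated figure does not reproduce.
- 80% power needs 34 per arm (68 in total) by the exact t calculation.
- n = 20 (40 in total): noncentrality 0.7 × √10 = 2.214, df 38, critical t 2.024, power 57.8%.

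The sample-size error is a separate matter. It is used here only because it sets the true starting point: 57.8%, with no power to spare.

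**Step 2: add a pre-dose covariate.** ANCOVA multiplies the residual SD by √(1 − r²) and costs one degree of freedom:

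- noncentrality = 0.7 × √10 / √(1 − r²), df 37, critical t 2.026
- 95% CI half-width, in units of the outcome SD = 2.026 × √0.1 × √(1 − r²)

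Without a covariate the half-width is 2.024 × √0.1 = 0.64 SD.

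| Assumed r | √(1 − r²) | Noncentrality | Power | CI half-width (SD) |
|---|---|---|---|---|
| no covariate | – | 2.214 | 57.8% | 0.64 |
| 0.1 | 0.995 | 2.225 | 58.2% | 0.64 |
| 0.2 | 0.980 | 2.259 | 59.5% | 0.63 |
| 0.3 | 0.954 | 2.320 | 61.8% | 0.61 |
| 0.5 | 0.866 | 2.556 | 70.2% | 0.55 |
| 0.7 | 0.714 | 3.100 | 85.5% | 0.46 |

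Setting power to 80% and solving for r gives about 0.64.

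**Step 3: would a change score do as well?** The standardized effect for a change score is 0.7 / √(2(1 − r)). With 20 per arm and df 38, power is 44.6% at r = 0.3, 57.8% at r = 0.5 and 79.5% at r = 0.7. Below r = 0.5 a change score does worse than no baseline at all, and at each of these three values it does worse than ANCOVA.

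**The case against.** Three stronger readings are tempting, and the documents do not support them.

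*A free driving baseline is thrown away.* The pre-dose drive is described only as practice and a sickness screen. Its course is not given, no brake test is mentioned for it, and nothing says it is logged. The statement about downloading data describes what the simulator can do, in the paragraph on the post-dose drive. No recorded baseline exists to be discarded; one would have to be set up.

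*A CBD effect cannot be told apart from chance differences in driving skill.* In a randomized comparison with placebo, the post-dose difference estimates the drug effect without bias, and the standard error already allows for chance imbalance. The loss is in precision.

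*Aim 3 is unsound because it sets a driving level against change scores.* Relating driving performance to changes in the tests is how Table 2 defines that aim. Replacing the level with a change in driving would be worse: the two drives differ in length, course, familiarity and timing relative to meals, so a change would mix those differences with any drug effect.

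Other objections carry weight. The plan chose deliberately to study driving between groups only, and it calls the trial exploratory. Driving history, PVT and SRT are collected before dosing and carry some related information. A short first exposure to the simulator includes learning, so r may be modest, and at r of 0.2 or less the gain is negligible. Lane departures and collisions, two of the four driving measures, gain nothing from the proposal.

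What remains is that the participant, the simulator and the time slot are all in place before dosing. The burden argument, which the plan uses to prefer a parallel design to a cross-over, does not explain leaving that drive unmeasured.

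**Conclusion.** The point holds as a missed gain in precision, not as a flaw in validity. The plan provides for no pre-dose driving measure, and the comparison of driving between arms has no driving covariate. At the plan's effect size, a covariate would move power from 57.8% to between 58.2% (r = 0.1) and 85.5% (r = 0.7), and the interval half-width from 0.64 SD to between 0.64 and 0.46 SD. The planned 40 participants would reach 80% power only if r were about 0.64 or more, so the covariate should not be presented as a cure for the sample size.

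These figures rest on an assumed r, on no dropout, on roughly normal outcomes with the same correlation in both arms, and on the effect size of 0.7, which the plan states for reaction time. They ignore the small further loss when the covariate is unbalanced by chance. The change is worth making because it is cheap, not because its benefit is assured.

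**What to change.** 1. In the consent, screening and baseline paragraph, specify that the existing 10-minute pre-dose drive includes a standard constant-speed segment and a short brake-reaction block, the same for everyone, and that the data file is saved.
2. In Table 2, Aim 1, add pre-dose SDLP and pre-dose mean BRT as baseline variables.
3. In the SAP, prespecify ANCOVA for SDLP and for mean BRT, each with its own pre-dose value as covariate, whether or not the arms look different at baseline. Say how skewed data will be handled (for example, by a log transformation), because the Mann-Whitney fallback takes no covariate.
4. Do not use change scores for the arm comparison. Keep Aim 3 on the post-dose driving level, optionally adjusted for the pre-dose value.
5. Leave lane departures and collisions as post-dose measures only.

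The cost is some scenario set-up, a saved file per participant and a few lines of text. No extra visit or staff is needed. The sponsor should confirm that the added segments fit within the 10 minutes and leave the drive's use as a sickness screen intact. A first-exposure drive is a noisy baseline. Learning before randomization affects both arms alike, so it limits the gain without biasing the comparison.

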These tests have all been deemed valid and reliable instruments and have been described in detail elsewhere. The tests will be administered by trained study personnel via a computer tablet and/or paper and pencil; personnel will then transfer the collected data to a secure, electronic database. Participants will also be given a standardized breakfast after baseline assessment.

**Allocation, Randomization and Blinding.** Participants will be randomized immediately after baseline assessments are completed to the CBD (N=20) or placebo group (N=20) using a sex-stratified 1:1 random block design to ensure equal distribution among treatment groups and sex. The participant and the PI will be unaware of group assignment (i.e. double-blind). [name], who will not have contact with participants, will generate a randomized assignment master list and provide sequentially numbered envelopes containing group assignment to the team member that helps consent participants. This team member will assign the unique number from the next envelope in sequence as the participant's study identification number and will record the participant's information in a secure, electronic master database.

**Intervention.** Protocol A consists of a 300 mg dosage of CBD oil which will be consumed orally. This dosage was chosen as it has been used in other studies consisting of both healthy and clinical populations and is well-tolerated with no major adverse events. CBD will be obtained from Zatural, a CBD manufacturer from Eden, Idaho. The CBD oil will be tested by Botanacor Laboratories (Denver, CO) for microbials, potency, heavy metals, trace THC, pesticides, and residual solvents to ensure purity, label accuracy, and safety; copies of laboratory reports will be maintained on premise. Protocol B is a placebo matched on appearance to the treatment (i.e., avocado oil potentially colored with food coloring). Both the CBD oil and placebo will be matched on taste (i.e., peppermint-flavored oil) prior to dispensing to each participant. After consumption of the respective protocol drug, the participant will be given a standardized meal and will then wait for 120 minutes to allow for digestion and for CBD to begin taking effect; this time frame was chosen based on the pharmacodynamics of CBD along with the consideration of participant burden (max absorption 2-5 hours). Next,

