**Figure 2**

PVT, SRT and complete an end of study questionnaire. The questionnaire will inquire about acceptability and tests of blinding.

**Participant Compensation and Safety.** All individuals who complete the study will receive a \$50 -gift card for their time and participation. All participants will be encouraged to report any adverse events (AE) to study staff during and after their participation in the study (i.e., up to 24 hours afterwards) and a physician ([name]) is available if needed. However, the half-life of consumed CBD is approximately 17 hours. The PI will report AEs to the WVU Institutional Review Board (IRB). All study personnel will have completed Human Subjects Training and the PI will obtain WVU IRB approval prior to study inception. As part of the inclusion criteria of the study, participants will be required to have a friend take them home after testing or they must agree to be transported home by study staff. We will also advise all study participants not to drive 24 hours post-testing for safety purposes.

**Data Collection, Management and Analysis.** All collected data will be entered by study staff into the secure, de-identified database and maintained in accordance with WVU IRB and Information Technology. All analyses will be performed in SAS (Cary, NC). The variables to be collected and their source are summarized in **Table 2**. Missing data will be multiply imputed to allow inclusion of all participants regardless of compliance. We will perform both an intent-to-treat analysis based on initial assignment and a protocol analysis, excluding those who fail to complete the study. Both between and within-group analyses will be conducted. Demographic characteristics and driving habits will be compared between groups via descriptive statistics to ensure proper randomization; we will also investigate

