tests of blinding by comparing accuracy of group assignment (perceived group assignment will be asked on end of study survey). If differences are noted, models can be adjusted. For between group effects, the data will be compared using Student's T-tests and/or ANOVA for continuous variables if the data are normally distributed; if non-normally distributed a Mann-Whitney test may be utilized. For within group effects, the data will be compared using paired Student's T-tests (for normally distributed continuous paired observations ) or Wilcoxon signed-rank test (for those continuous paired observations not normally distributed). We will perform a correlation using Pearson's R test between the variables collected for Aims 1 and 2, both between and within groups, to assess whether driving performance is

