## Statistical Analysis Plan

All collected data will be entered by study staff into the secure, de-identified database and maintained in accordance with WVU IRB. All analyses will be performed in SAS (Cary, NC). The primary outcome of this study will be driving performance, including number of lane departures, standard deviation of lateral position (i.e., weaving), mean brake reaction time, and number of collisions (Aim 1). Secondary outcomes will be pre-post changes in well-validated measures of mental sedation (SSS, VAMS) and cognitive function (DSST, TMT, PVT, SRT) (Aim 2). The variables that will be collected and their source are summarized in Table 2. Missing data will be multiply imputed to allow inclusion of all participants regardless of compliance. We will perform both an intent-to-treat analysis based on initial assignment and a protocol

analysis, excluding those who fail to complete the study. Both between and within-group analyses will be conducted. Demographic characteristics will be compared between groups via descriptive statistics to ensure proper randomization; we will also investigate tests of blinding by comparing accuracy of group assignment (perceived group assignment will be asked on end of study survey). For between group effects, the data will be compared using Student's T-tests and/or ANOVA for continuous variables if the data are normally distributed; if non-normally distributed a Mann-Whitney test may be utilized. For within group effects, the data will be compared using paired Student's T-tests (for continuous paired observations which are normally distributed) or Wilcoxon signed-rank test (for continuous paired observations which are not normally distributed). We will perform a correlation using Pearson's R test between the variables collected for Aims 1 and 2, both between and within groups, to assess whether driving performance is correlated with psychological or cognitive testing measures. Data will also be analyzed via sex.

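### Randomisation is stratified by sex, but the between-group tests leave sex out and the test battery is not adjusted for its baseline score: precision forgone, not an invalid analysis

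*Combined protocol and SAP*

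**What the plan says.** **Allocation.** Under Allocation, Randomization and Blinding, participants are assigned "using a sex-stratified 1:1 random block design to ensure equal distribution among treatment groups and sex", 20 per arm.

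**Between-group tests.** Data Collection, Management and Analysis and the Statistical Analysis Plan give the same methods: "T-tests and/or ANOVA for continuous variables if the data are normally distributed; if non-normally distributed a Mann-Whitney test may be utilized". No factor or covariate is named. The Sample Size paragraph also has no sex term: "using a two-sided, two-sample equal variance t-test achieves 80% power to reject the null hypothesis of equal means".

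**Sex in the analysis.** The Statistical Analysis Plan adds "Data will also be analyzed via sex", and the earlier section has a near-identical line. Neither gives a method. The wording marks this as something additional to the main comparison.

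**Baseline scores.** Consent, Screening, and Baseline Assessments has VAMS, SSS, TMT, DSST, PVT and SRT taken before dosing. The secondary outcomes are their pre-post changes. No baseline adjustment is specified.

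**Optional adjustment.** Data Collection, Management and Analysis says "Demographic characteristics and driving habits will be compared between groups via descriptive statistics to ensure proper randomization". It then describes a blinding check ("perceived group assignment will be asked on end of study survey") and continues: "If differences are noted, models can be adjusted". It names no covariate, threshold or model. The Statistical Analysis Plan repeats both checks but omits the adjustment sentence.

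**The concern.** Stratifying by sex balances the arms on sex. That gains precision only if the analysis also removes the between-sex variation from the error term. Otherwise the variation stays in the standard error although it no longer contributes to the difference between arms. The standard error is then too large, the test rejects less often than its nominal level, and power falls.

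The same reasoning applies, usually more strongly, to a pre-dose score on the same test.

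The adjustment sentence adds a smaller issue. As written, chance imbalance on an unlisted variable, judged without a criterion, would decide which model is used for the driving outcomes.

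**Working it through.** **1. The plan's own figure.** The Sample Size paragraph gives 26 in total for 80% power at d = 0.7, two-sided alpha 0.05. The exact two-sample t-test gives 40.3% at 26 and 57.8% at 40; 80% needs 34 per arm (68 in total). That mismatch is a separate matter. It is noted only because 57.8%, not 80%, is the right reference for N = 40 below.

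**2. Inputs.** From the documents: 20 per arm, sex-stratified 1:1, d = 0.7, alpha 0.05 two-sided. Assumed: normal outcomes; d in within-sex SD (set to 1); the same sex split in both arms; sex difference s = 0, 0.3, 0.5 or 1.0 SD; pre-post correlation rho = 0.3, 0.5 or 0.7.

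**3. Sex in the model.** Noncentrality = 0.7 × √(20/2) = 2.21. With 37 df, power is 57.8% whatever s is. Without a sex term and with s = 0 (38 df) it is also 57.8%.

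**4. Sex left out.** With f and m of each sex per arm, the expected pooled variance is about 1 + k·s²/38, where k = (2f × 2m)/40. For a 10/10 split k = 20 × 20/40 = 10. At s = 1.0 the variance is 1 + 10/38 = 1.263, the SD is 1.124, the effective d is 0.7/1.124 = 0.623, and power is about 48%. Simulation (200,000 trials per setting) gives:

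| Split per arm | s = 0 | 0.3 | 0.5 | 1.0 |
|---|---|---|---|---|
| 10/10 power | 57.9% | 57.0% | 55.4% | 48.2% |
| 14/6 power | 57.9% | 57.0% | 55.7% | 49.7% |
| 16/4 power | 57.7% | 57.5% | 56.4% | 51.7% |
| 10/10 type I error | 5.0% | 4.7% | 4.3% | 2.8% |

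Against 57.8%, the loss is at most 0.8 points at 0.3 SD, 1.4 to 2.4 at 0.5 SD (2 to 3 if the percentages are rounded first), and 6.1 to 9.6 at 1.0 SD.

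**5. Rank tests (normal outcomes, 10/10).** Over the same four values of s, Mann-Whitney has 55.0/54.5/53.0/45.2% and the sex-stratified van Elteren test 54.4/54.8/55.0/54.8%. The stratified test costs 0.6 points when sex is irrelevant and gains 9.6 at 1.0 SD.

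**6. Baseline score.** Take d = 0.7 in SD of the post-dose score. A change score has SD √(2(1 − rho)), so its effective d is 0.7/√(2(1 − rho)). A baseline-adjusted model has residual SD √(1 − rho²), so its effective d is 0.7/√(1 − rho²).

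| rho | Change score: d, simulated power | Sex + baseline: d, simulated power |
|---|---|---|
| 0.3 | 0.592, 44.7% | 0.734, 60.5% |
| 0.5 | 0.700, 57.6% | 0.808, 69.0% |
| 0.7 | 0.904, 79.3% | 0.980, 84.2% |

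The adjusted model's type I error stays at 5.0% to 5.1%.

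**7. The adjustment sentence.** With 5 to 10 baseline variables, chance alone would trigger adjustment in 22% to 40% of trials if a difference means p < 0.05, 48% to 73% if it means 0.5 SD, and 98% to 100% if it means 0.2 SD. Adjusting whenever triggered gives a type I error of 2.9% to 5.0%.

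**The case against.** The strongest reply is that little is lost. The unadjusted estimate is unbiased, the test errs on the safe side, no sex effect is documented, and the cost is 1 to 2 points unless sexes differ by nearly a full SD. The trial calls itself exploratory. All of that stands and sets the weight of the point.

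A second reply is that ANOVA on two arms alone merely repeats the t-test, so naming ANOVA beside an analysis by sex may allow a sex factor. It may, but the plan does not say so, and neither the t-test nor Mann-Whitney can carry one. Nor is the plain t-test in the Sample Size paragraph a fault in itself; that is ordinary when no sex effect is known.

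A third reply is that comparing change scores is valid. It is; baseline adjustment is preferred for efficiency, not to correct an error.

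Three stronger readings are tempting, and the documents do not support them:

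- **The open adjustment sentence inflates type I error.** Adjusting when an imbalance is seen does not. Inflation (5.5% to 7.3% in simulation) arises only if the more favourable of two analyses is reported, which the plan does not describe.
- **The treatment guess will be used as a covariate.** The sentence does follow the blinding check, but it reads more naturally as referring to the baseline comparison. Any bias would also need guesses to follow sedation, by an amount the documents do not give.
- **Omitting sex costs about 15 points of power.** That needs sex to explain 30% of outcome variance, with d scaled to the total SD (58.5% against 73.1%). Nothing in the documents indicates so large a share.

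**Conclusion.** The point holds as one of efficiency. Sex is a stratification factor that the specified between-group tests do not use, and the battery's baseline scores are collected but not used for adjustment. The gain from including sex is small unless the sex difference approaches 1 SD, and essentially nothing is lost if there is none. The gain for the test battery is larger, about 5 to 16 points over the assumed correlations.

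These sizes rest on normal outcomes, 20 complete participants per arm and d = 0.7. They were not worked out for skewed counts, so the gain for lane departures and collisions is not quantified. The planned analysis is neither biased nor invalid, and the adjustment sentence is a gap in prespecification.

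**What to change.** - Include sex as a fixed factor in every between-group model.
- Where a rank test is used, including for skewed counts such as lane departures and collisions, use the sex-stratified Wilcoxon (van Elteren) test.
- For VAMS, SSS, DSST, TMT, PVT and SRT, also adjust the between-group model for the participant's baseline score.
- In Data Collection, Management and Analysis, replace the optional adjustment sentence with this fixed covariate set, and put the same wording in the Statistical Analysis Plan. Chance imbalance then does not choose the model.
- Report the treatment guess descriptively only.

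The cost is a change of wording with no new data: one degree of freedom for sex, one more for baseline in the battery models, and up to about 1 point of power for the van Elteren test if sex is not prognostic.
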